Clinical Safety	MDSS GmbH [name] [name], Germany [contact] [contact] Email: [contact]
Data Safety Monitoring Board (DSMB)	A list of members of the DSMB is filed separately in the TMF together with the DSMB charter.

SYNOPSIS

Title	A prospective, open-label, multicenter clinical investigation to assess the safety and performance of the ARGOS-IO system in patients with Primary Open Angle Glaucoma (POAG)
Study Number	ARGOS-02
Sponsor	Implandata Ophthalmic Products GmbH
Name of IMD	
ARGOS-IO System
 
The ARGOS-IO system is composed of the implant and its accessories:
 
Implant: ARGOS-IO pressure sensor implant
 
Accessories:
 
MESOGRAPH reading device, Implant Injector and telemetric Multiline Connector

Indication	Patients with Primary Open Angle Glaucoma (POAG) and indicated cataract surgery
Study Purpose	The purpose of this study is to evaluate the safety and performance of the ARGOS-IO system in patients with POAG and indicated cataract surgery.
Study Design	
This clinical investigation prospective, open-label, multicenter, single-arm clinical investigation will be conducted in two stages using a Simon two-stage design. Subjects will be enrolled as follows:
 
First stage: 11 patients
 
Second stage: 11 patients
 
An interim analysis will be performed when the 11 patients of the first stage have completed their 3 month follow-up visits. The trial will be stopped if 2 or more patients have experienced a serious adverse device events (SADE) at this time. Otherwise enrollment will be resumed and the trial continued until an additional 11 patients have been enrolled in stage 2 and received ARGOS-IO implants. A conclusion for safety will be made if in total no more than 2 of the total of 22 patients experience an SADE.

Sample Size Considerations	The primary aim of this study is to show “safety”, which will be evaluated based on the percentage of subjects who experience an SADE (= “non-safety”), as defined in the primary endpoints.

	
For the study as a whole, “safety” will be determined based on the following decision rule: if in stage 1 the non-safety event rate is greater than 25%, the trial will be stopped (type 1 error rate of 0.05). If the non-safety event rate is lower than 25%, the study will be continued into stage 2. It will be declared a success if the final non-safety event rate is less than 6% (type II error rate of 0.20) The calculation is based on a two-stage Simon design optimizing the minimum expected sample size with parameters $\alpha=0.05$, $\beta=0.20$, $p_0 = 0.75$, $p_1 = 0.94$.

Subject Population	
This study will enroll subjects with POAG and indicated cataract surgery until a maximum of 22 have undergone implantation with the ARGOS-IO pressure sensor.

Study Objectives	
Primary Objectives
 
Safety
 
To evaluate the safety and tolerability of ARGOS-IO pressure sensor implantation by assessing the incidence of SADEs in the 3 months immediately following implantation.
 
Performance
 
To evaluate the limits of agreement between measurements with the Goldmann Applanation tonometry (GAT) and the ARGOS-IO system between day 30 through day 180.
 
Secondary Objectives
 
Safety
 
 • To evaluate the safety and tolerability of ARGOS-IO pressure sensor implantation by assessing the incidence of adverse events and adverse device events between 3 months and 12 months following implantation. 
Performance
 
 • To evaluate the performance of the ARGOS-IO system up to 12 months after implantation.
Patient Selection	
Inclusion Criteria
 
Eligible subjects must meet all the following inclusion criteria:
 
 1. Mentally competent and willing to provide written Informed consent 2. Male or female aged ≥ 40 years ≤ 85 years on the day of screening

Female subjects of childbearing potential (not surgically sterilized or more than one year post-menopausal) must be willing to use adequate contraception throughout the trial and must have a negative pregnancy test (urine beta-hCG) within 24 hours prior to ARGOS-IO pressure sensor implantation.

3. Diagnosis of primary open-angle glaucoma (POAG) including high pressure glaucoma (HPG), normal pressure glaucoma (NPG) and ocular hypertension (OH) as defined by the European Glaucoma Society guideline (Heijl, Traverso, & al, 2008) requiring regular IOP measurements
4. Sufficiently controlled IOP
5. Phakic eyes
6. Only one eye per patient may be implanted with the ARGOS-IO implant
7. Cataract surgery indicated. The medical indication for a cataract operation must be given irrespective of the study participation. Potential study patients will be solicited for participation in the clinical trial only after the patient has given consent to the cataract operation
8. Pre-operative anterior chamber depth (ACD) ≥ 2.5 mm as measured from the corneal endothelium
9. Axis length > 22 mm
10. Endothelial cell density of the cornea ≥ 2000 cells/mm²
11. Subjects able and willing to attend all scheduled visits and comply with all study procedures

Exclusion Criteria

Eligible subjects must not meet any of the following exclusion criteria:

1. Any other type of glaucoma other than primary open-angle glaucoma as defined in inclusion criteria 3
2. Severe POAG patients with a macular degeneration and visual field loss of -20dB or worse
3. Exsudative age-related macular degeneration, instable macular degeneration 30 days prior to inclusion, or macular edema
4. Retinal detachment
5. Corneal diseases
6. Diabetes mellitus
7. Connective tissue diseases
8. History or evidence of severe inflammatory eye diseases (i.e. uveitis, retinitis, scleritis) in one or both eyes within 6 months prior to ARGOS-IO implantation

9. Intraocular surgical procedure(s) within 6 months prior to ARGOS-IO implantation or any surgical procedure such as refractive eye surgery that can affect the assessment of IOP by Goldmann Applanation tonometry
10. History of eye tumor
11. Ocular disease other than glaucoma that may affect assessment of visual acuity and/or IOP by Goldmann Applanation tonometry (choroidal hemorrhage or detachment, lens subluxation, thyroid ophthalmopathy)
12. Anterior chamber configuration that puts the subject at high risk to develop an angle closure glaucoma
13. History of extensive keloid formation
14. Severe dry eye syndrome
15. Subjects who will need to undergo ancillary procedures in the study eye at the time of implantation or during the post-operative study period
16. Any known intolerance or hypersensitivity to topical anesthetics, mydriatics, plaster or silicone (component of the device)
17. Existence of other active medical eye implant and/or other active medical implants in the head/neck region
18. Any contraindication for IOL implantation such as choroidal hemorrhage, concomitant severe eye disease, excessive vitreous loss, extremely shallow anterior chamber, microphthalmos, non-age-related cataract, posterior capsular rupture, severe corneal dystrophy, untractable IOP, zonular separation, color vision deficiencies
19. Severe generalized disease resulting in a life expectancy shorter than a year
20. Any clinical evidence that the investigator feels would place the subject at increased risk with the placement of the device
21. Currently pregnant or breastfeeding
22. Participation in any study involving an investigational drug or device within the past 30 days or ongoing participation in a study with an investigational drug or device
23. Patients who are not suitable for the study based on the surgeon's evaluation
24. Patients unable or unwilling to understand or comply with required study procedures
25. Patients with psychiatric disorders influencing their judgement or autonomy

	
26. Subject and/or an immediate family member is an employee of the investigational site directly affiliated with this study, the sponsor or the contract research organization.
 
27. Enrollment of the fellow eye in this clinical study

Study Procedures	
Screening (SC)
 
Consecutive potential subjects will undergo informed consent process up to 28 days prior to surgery. Consenting subjects will be screened. Screening visit will include:
 
 • Demographics • Medical history • Pregnancy tests for females of child-bearing potential 
General
 
 • Optical biometry (IOL Master) • Visual acuity (ETDRS) • Perimetry • Concomitant medication 
Anterior segment measurement
 
 • Slit-lamp biomicroscopy • Optical coherence tomography (OCT) • Confocal Microscopy • Gonioscopy 
Posterior segment measurement
 
 • Biomicroscopy • Optical coherence tomography (OCT) • Fundus photography 
IOP measurement
 
 • Goldmann Applanation tonometry (GAT) 
Surgery (V01)
 
On day of surgery or one day prior to surgery, subjects will again be assessed for eligibility requirements including pregnancy testing for females of childbearing potential. Subjects who continue to meet eligibility requirements will undergo cataract surgery with ARGOS-IO pressure sensor implantation using the implant injector and standard clinical procedures. If it

becomes apparent during the surgery that the subject is not a suitable candidate for the ARGOS-IO pressure sensor implant, the cataract surgery will be carried out using standard of care and the subject removed from the study.

At Visit 01, data will be collected regarding:

General

- Implantation procedure questionnaire (surgeon)
- AE/ADE/SAE/SADE
- Concomitant medication
- Device deficiency

Follow-up (V02 to V11)

The follow-up period after surgery will consist of 10 visits (Day 1 until D360). The examinations performed at each visit are listed without mentioning the single visit in parentheses. Examinations that are carried out only at distinct visits are indicated in parentheses. The follow-up visits will include :

General

- Optical Biometry (IOL Master) (V09)
- Visual acuity (EDTRS)
- Perimetry (V07, V09, V11)
- External Eye Photography
- User acceptance questionnaire (patient) (V11)
- User acceptance questionnaire (investigator) (V11)
- AEs/ADEs, SAEs/SADEs
- Concomitant medication
- Device deficiency

Anterior Segment

- Slit-lamp biomicroscopy
- Optical coherence tomography (OCT) (V07, V09, V11)
- Confocal Microscopy (V07, V09, V11)
- Gonioscopy (V07, V09, V11)

Posterior segment measurement

- Biomicroscopy
- Optical coherence tomography (OCT) (V07, V09, V11)

	
 • Fundus photography (V07, V09, V11) 
IOP measurement
 
 • Goldmann Applanation tonometry (GAT) • ARGOS-IO system measurement 
Measurements will be performed in series of 1 GAT measurement followed by 3 consecutive measurements with the ARGOS-IO system, with not more than 10 minutes between the GAT and the ARGOS-IO system measurements of a single series and a minimum of 60 minutes between the end of the one series and the start of the next.
 
At V02, V03 and V04 only GAT measurements will be made (at beginning and end of visit).
 
At V06, V08 and V10 two series of measurements will be made (at beginning and end of visit).
 
At visits V05, V07, V09 and V11 four series of measurements will be made.
 
 • ARGOS-IO system self-measurement at home (Visit 05 to Visit 11)
Data Analysis and Statistics	
Primary Endpoints
 
Safety
 
 - Number of patients experiencing a device related SAE defined as any adverse event that both 
 ○ Is considered by the Investigator to have a possible, probable or definite relationship to the device and ○ That meets any of the following criteria of a serious adverse event: 
 ▪ Resulted in death, permanent damage or disability or a congenital anomaly ▪ Was life threatening ▪ Required hospitalization or intervention to prevent permanent impairment or damage 
Performance
 
 - Agreement between measurements made using GAT and the ARGOS-IO system from V05 (day 30) through V09 (day 180). If multiple ARGOS-IO system measurements have been made at time points for which paired GAT/ARGOS-IO system measurements are to be compared, the mean of the replicate ARGOS-IO system measurements will be used for

agreement evaluation. The agreement evaluation is based on the assumption, that the measurements are constant over the measurement period.

Secondary Endpoints**Safety**

- Incidence, nature, severity and seriousness of observed adverse events and adverse device events in the 3 months following implantation.
- Incidence, nature, severity and seriousness of observed adverse events and adverse device events in the 6 months following implantation.
- Incidence, nature, severity and seriousness of observed adverse events and adverse device events in the 12 months following implantation.

Performance

- Limits of agreement between measurements made using GAT and the ARGOS-IO system from V05 (day 30) through V11 (day 360).
- Performance of the ARGOS-IO system after 6 months by means of incidence of observed device malfunctions.
- Performance of the ARGOS-IO system after 12 months by means of incidence of observed device malfunctions.
- User acceptance of the implantation procedure by means of evaluation of implantation procedure questionnaires (investigators).
- User acceptance of the ARGOS-IO system at the investigational site by means of evaluation of investigator acceptance questionnaires (investigators).
- User acceptance of the ARGOS-IO system at home by means of evaluation of patient acceptance questionnaires (patients).
- Daily IOP self-measurement profiles (patients).

Definition of the analysis populations

The safety population comprises all subjects for whom ARGOS-IO pressure sensor implantation was attempted, whether or not the implantation was successful. In this clinical investigation the intention-to-treat (ITT) population comprises the same subjects as defined in the safety population.

	
Statistical analysis
 
Safety analysis
 
Incidence of SADE in the 3 month period immediately following implantation. The decision on safety follows the rule of the SIMON optimum two-stage design (parameters: $\alpha=0.05$, $\beta=0.20$, $p_0 = 0.75$, $p_1 = 0.94$, minimize expected samples size). A corresponding 95% confidence interval will be given for the portion of SADE within the safety population. The confidence interval for the SADE rate will be calculated using the method proposed by Koyama (Koyama & Chen, 2008). These calculations will be based on the number of patients experiencing an SADE.
 
Moreover, safety will be described in detail by frequency, seriousness, severity, nature and duration of events. Adverse events and the number of subjects reporting adverse events will be tabulated by system organ class and preferred terms. Adverse device events, device deficiencies and the number of subjects reporting adverse device events and device deficiencies will be tabulated by event/deficiency description.
 
Performance analysis
 
The Bland-Altman approach will be used to establish limits of agreement between the IOP measurements from GAT and the ARGOS-IO system within the ITT population. Two-sided 95% confidence intervals will be calculated accounting for repeated measurements based on the method proposed by Zou (2011).
 
Other secondary performance endpoints will be analyzed by descriptive and explorative statistical methods.
 
Interim Analysis
 
An interim analysis to assess SADE will be performed, when the first 11 patients have completed the 3 month follow-up visit.

Safety Monitoring	
A data safety monitoring board (DSMB) will be established prior to enrollment of the first patient. The DSMB is to review the safety data, including SAEs/SADEs, on a regular basis and will advise on any changes required in the conduct this clinical investigation. The DSMB will also review the data of the interim analysis and give recommendations to the Sponsor to either continue the clinical investigation (with or without an amendment of

	the clinical investigation plan) or to stop enrolment into the clinical investigation based on safety concerns.
Data Collection	Data will be collected using a paper-based Case Report Form (CRF).

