8. DESIGN OF THE CLINICAL INVESTIGATION

8.1 General Aspects

8.1.1 Description of the type of clinical investigation

The trial will be conducted as an open, prospective, multicenter single-arm clinical trial using the two-stage design described by Simon (Simon, 1989). In the first stage, 11 patients will have an ARGOS-IO pressure sensor implanted, after which enrollment will be halted until the patients have completed their 3 months follow-up visits and an interim analysis has been performed. The interim analysis will be reviewed by the DSMB. If two or more of these 11 patients in the first stage are found to have had an SADE, further enrollment into the study will be stopped. If not, enrollment will resume until another 11 patients have had an ARGOS-IO pressure sensor implanted. If two or fewer of the total 22 patients experience an SADE, a conclusion for safety will be made at the 5% significance level. A corresponding 95% confidence interval for the SADE rate will be calculated according to the procedure of Koyoma (2008).

 Implandata Ophthalmic Products GmbH	Clinical Investigation Plan ARGOS-02	Revision C
		Page 60 of 106

All patients who receive an ARGOS-IO implant will return for 10 follow-up visits to the clinic (day 1, 3, 10, 30, 60, 90, 120, 180, 240, 360) during the 12-month post-surgical period (see Table 6: Assessment Schedule). To allow comparison of the IOP measurement methods, IOP measurements will be made at every visit with GAT and with the ARGOS-IO systems beginning at V5 (day 30).

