8.3.3.3 Premature subject withdrawal

Subjects will be informed that they have the right to withdraw from the study at any time. The investigator must determine whether voluntary withdrawal is due to safety concerns.

All subjects who withdraw from the study after implantation and before completing the follow-up visits per protocol will be considered to be drop-outs. Subjects who drop-out or are withdrawn after implantation will not be replaced. Unless the patient revokes his/her permission to use it, any data collected up to the point of the patient's withdrawal will be included in the safety analysis. The data of all subjects who undergo implantation of the ARGOS-IO pressure sensor will be included in the efficacy analysis under the Full Analysis Set.

A patient will be withdrawn for any of the following reasons:

- The patient withdraws informed consent.
- It is determined during surgery that the patient is not feasible for ARGOS-IO pressure sensor implantation.
- The ARGOS-IO pressure sensor must be removed or replaced for any reason.

If the patient permits, all end-of-study assessments indicated in the visit schedule should be performed for implanted early discontinuing subjects.

Any subject who has been discontinued from the study because of an AE related to a study device or procedure will be followed as deemed appropriate by the investigator until resolution or stabilization of the event. This will be documented in the medical chart and in the CRF. Any patient who has been discontinued from the study because of an AE not related to a study device or procedure will be followed as deemed appropriate by the investigator.

 Implandata Ophthalmic Products GmbH	Clinical Investigation Plan ARGOS-02	Revision C
		Page 67 of 106

The investigator will classify the termination reason of each subject at the end of the study in the termination page of the CRF according to the following:

- AE
- Non-compliance with clinical investigation plan (CIP)
- Lost to follow up
- Voluntary withdrawal not for AE
- Other reason.

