8.4.4.5 AEs/ADEs/SAEs/SADEs

Starting with the implantation of the ARGOS-IO pressure sensor, all AEs/ADEs/SAEs/SADEs will be recorded.

	Clinical Investigation Plan ARGOS-02	Revision C
		Page 71 of 106

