9.2 Sample Size Calculation

The sample size calculation was based on the study's purpose of establishing safety.

To minimize the required sample size and consequently the number of patients exposed to risk while at the same time maximizing the chances of detecting safety events, a two-stage design based on the rate of non-events was chosen (Simon, 1989). The event of interest was defined as a serious device-related adverse events (SADEs). Based on a probability of non-events of $p_0=0.75$ for the first stage and an overall acceptable probability of $p_1=0.94$, a sample size of at least 11 evaluable patients in the first stage and additional 11 patients in the second stage are required. This maintains a type 1 error probability of 5% and the power of 80% based on minimizing the maximal sample size and results in an expected sample size of 13.2 patients.

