9.3 Level of significance and the power of the clinical investigation

Significance level is set to 0.05, Power to 80%.

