9.11 Datasets to be analyzed

9.11.1 Safety population

The data of all patients, with successful implantation of the ARGOS-IO implant, will be used for the safety evaluation.

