4.1 Analysis Populations

Within the framework of this study, the following two main populations are analysed:

- **Safety Population:** consists of all patients with attempted implantation of the ARGOS-IO implant, whether or not successful.
- **Full Analysis Set (FAS):** The FAS population comprises all subjects in whom an ARGOS-IO pressure sensor was successfully implanted. Measurements recorded by the patient will not

be included into the evaluation of the FAS population. Additional information about the drop-outs: all patients who revoke their consent and agreement preoperatively will be regarded as screen failures and will not be included in the statistical evaluation. All patients who revoke their consent and agreement postoperatively will be considered withdrawals and their data will be evaluated in the safety analysis.

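### Attempted but unsuccessful implantations are in the safety population, yet they have no scheduled 3-month follow-up and no scoring rule

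*Protocol*

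**What the plan says.** **Who is analysed.** The CIP synopsis (analysis populations) includes failed attempts in the safety population. SAP 4.1 agrees: the population "consists of all patients with attempted implantation of the ARGOS-IO implant, whether or not successful". SAP 6.2 and 7.2 count patients with a SADE within 3 months and apply the decision rule and confidence interval to that population. CIP 9.11.1 differs: "The data of all patients, with successful implantation of the ARGOS-IO implant, will be used for the safety evaluation".

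**What happens to a failed attempt.** The synopsis (Study Procedures, Surgery) provides that, if the patient proves unsuitable during surgery, "the cataract surgery will be carried out using standard of care and the subject removed from the study". CIP 8.3.3.3 and SAP 2.6 list the same situation as a reason for withdrawal. CIP 8.5.2 covers an implantation that the surgeon abandons.

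**Who is followed.** CIP 8.1.1 says: "All patients who receive an ARGOS-IO implant will return for 10 follow-up visits to the clinic". The addendum's amended 8.1.1 and SAP 2.3 repeat this. Under CIP 8.3.3.3, end-of-study assessments "should be performed for implanted early discontinuing subjects".

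**When events are recorded.** CIP 8.4.4.5 says: "Starting with the implantation of the ARGOS-IO pressure sensor, all AEs/ADEs/SAEs/SADEs will be recorded". CIP 11.1.3 starts at surgery instead, and ends at discharge from the study.

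**The concern.** The analysis population calls for a 3-month SADE status in patients for whom the conduct sections plan no contact after the operation. These patients may still have had device-related exposure: CIP 6.6 names the larger incision, the iridectomy and the longer operation, and CIP 11.1.2.1 counts effects of implantation as device effects. CIP 5.2 reports findings from ARGOS-01 at days 1 to 7, which is later than the only study visit such a patient is sure to have.

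The success limit is 2 events, and under the addendum each SADE halts enrolment and calls the DSMB. One event that nobody is scheduled to look for therefore matters, both for the conclusion and for the protection of later patients.

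The plan foresees the case: SAP 4.2 lists successful implantation, yes or no, as a subgroup variable for the co-primary endpoints. The *no* group would have no scheduled post-operative data.

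**Working it through.** **Inputs.** SADE rates of 25% (1 − 0.75) and 6% (1 − 0.94), from CIP 9.2. Rule: continue if at most 1 of 11 has a SADE, succeed if at most 2 of 22 do (CIP Table 7, SAP Table 2). CIP 9.3: "Significance level is set to 0.05, Power to 80" per cent. The addendum drops the two-stage structure but keeps 2 of 22; SAP 2.1 and 2.10 keep the stage 1 stop. The number k of failed attempts with no 3-month status is my assumption (0, 1 or 2).

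**Step 1. Reproduce the design.** Type I error = P(X1=0)·P(X2≤2) + P(X1=1)·P(X2≤1).
- At 25%: 0.0422 × 0.4552 + 0.1549 × 0.1971 = 0.0497.
- Power, same formula at 6%: 0.5063 × 0.9752 + 0.3555 × 0.8618 = 0.800.
- Expected sample size at 25%: 11 + 11 × 0.1971 = 13.17, against 13.2 in CIP 9.2.
- One-stage rule: P(X≤2 of 22) at 25% = 0.0606.

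The plan's figures reproduce.

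**Step 2. How would an unobserved failed attempt be scored?** No section says.
- SAP 7.2 counts patients with a SADE in the safety population, and SAP 3 uses all patients in the population as the denominator. Together these make the patient event-free by default.
- SAP 5.1 restricts analyses to observed cases without imputation, which could instead exclude the patient.
- SAP 5.2 recalculates the critical value only for losses after implantation.
- CIP 8.1.5 treats anyone withdrawn up to implant as a screen failure to be replaced. The addendum's 9.1 enrols until 22 have received implants. Both suggest that failed attempts come on top of the 22.

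**Step 3. If k patients are among the 22 and scored event-free.** Only 22 − k patients can contribute an event. For k = 1:
- missing in stage 2: 0.0422 × 0.5256 + 0.1549 × 0.2440 = 0.0600
- missing in stage 1: 0.0563 × 0.4552 + 0.1877 × 0.1971 = 0.0626

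For k = 2, with both in stage 2 or both in stage 1:
- 0.0422 × 0.6007 + 0.1549 × 0.3003 = 0.0719
- 0.0751 × 0.4552 + 0.2253 × 0.1971 = 0.0786

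One-stage: P(X≤2 of 21) = 0.0745 and P(X≤2 of 20) = 0.0913.

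| k | Type I error, two-stage | Type I error, one-stage |
|---|---|---|
| 0 | 5.0% | 6.1% |
| 1 | 6.0–6.3% | 7.5% |
| 2 | 7.2–7.9% | 9.1% |

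**Step 4. If they are additional to 22 implanted patients.** The rule still acts on 22 patients with scheduled follow-up, so its error rate is unchanged. Only the reported rate is diluted: 2/22 = 9.1% becomes 2/23 = 8.7% or 2/24 = 8.3%.

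**Step 5. If they are excluded from the 22 without replacement.** With 21 evaluable patients (one lost in stage 2), keeping the limit at 2 gives the same 6.0% as in step 3. Lowering it to 1 gives a type I error of 0.0422 × 0.2440 + 0.1549 × 0.0563 = 0.019 and power of 0.5063 × 0.8824 + 0.3555 × 0.5386 = 0.638. Exclusion alone does not restore the design; replacement or full ascertainment does.

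**The case against.** The best defence is that these patients are not simply lost. Events at the surgery visit are collected (synopsis, V01). A subject discontinued because of a device- or procedure-related event is followed, as the investigator sees fit, to resolution or stabilization (CIP 8.3.3.3), and all SAEs are followed likewise (CIP 12.13). Patients are told to report SAEs promptly during the study (CIP 8.7.2). A SADE seen at surgery would thus be known, counted and taken to the DSMB. This stands, and a reader who inferred that there is no follow-up at all would go too far. But these provisions follow events already known, or apply while the patient is in the study. None looks for a new event after withdrawal.

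A reader might also infer that the plan counts these patients as event-free. It does not say so. That is one default reading; exclusion is another, and under CIP 9.11.1 they would not be in the population at all.

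A third tempting step is to treat a missed event as raising the limit from 2 to 3 of 22. That assumes an event is certain to be missed whenever three occur. The proper comparison is one unobserved patient, as in step 3, and it moves the error by about one percentage point.

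Two further points are fair. The synopsis sentence also covers patients stopped before any insertion was tried, and *attempted* is never defined. And the SAP cites CIP Rev. G, while the protocol text available is Rev. C with an addendum, so the clash between SAP 4.1 and CIP 9.11.1 may be one of versions. The clash between the Rev. C synopsis and its own section 9.11.1 is not.

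**Conclusion.** The point holds as a gap in ascertainment and definition. Under the synopsis and SAP 4.1, a patient with a failed attempt is in the population for the primary safety decision but has no scheduled contact that would reveal a first serious device-related event between discharge and month 3. Under CIP 9.11.1 the same patient is left out. Neither reading secures the event for the limit of 2 or for the DSMB trigger.

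The numerical effect is modest and conditional. It rests on an assumed number of failed attempts and on their being among the 22 and scored event-free: 5.0% to 6.0–6.3% for one such patient and 7.2–7.9% for two under the two-stage rule, or 6.1% to 7.5% and 9.1% under the one-stage rule. If they are additional to 22 implanted patients, as CIP 8.1.5 and the addendum suggest, the error rate does not move and only the reported rate is diluted. The case for a change rests mainly on missed detection in device-exposed patients, not on these percentages.

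**What to change.** 1. Define *attempted* (for example, by a stated step of the implantation procedure), so that patients stopped before it are clearly outside the safety population.
2. Reconcile CIP 9.11.1 with the synopsis and SAP 4.1 to one safety population of all attempted implantations.
3. Amend the synopsis, CIP 8.3.3.3 and SAP 2.6 so that attempted patients stay in the study for AE and SADE ascertainment to 3 months, by visit or telephone and without ARGOS readings. State that their SADEs count toward the limit and trigger the DSMB review.
4. State whether they are within or additional to the 22. Treat any without 3-month status as non-evaluable, not event-free. If they are within the 22, extend the recalculation in SAP 5.2 to them or replace them (step 5).
5. Align the start of AE recording in CIP 8.4.4.5 with CIP 11.1.3.

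The cost is wording in the CIP and SAP, plus AE contacts to 3 months for what are probably very few patients. The sample size and the decision limit need not change if these patients are followed or are additional to the 22.
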